3 HUMAN SUBJECTS

3.1 Subject Population

Intervention participants will be identified in a consecutive manner at participating UPMC community-based PC practices, outpatient clinics and inpatient units. Study participants will include adult male and female T2DM patients, 18 to 75 years old, with T2DM and suboptimal glycemic control (HbA1c > 7.5%) who are recommended to start titrating basal insulin and willing and able to use the MDC app.

The retrospective comparative group will be selected from eligible patients who previously were treated at the UPMC Diabetes Outpatient Clinics. This group will be chosen for two reasons. First, patients seen at the Diabetes Outpatient Clinic have the most robust data available regarding insulin titration, including HbA1c and FBG and, for many patients, BG meter readings. Secondly, this particular group establishes a standard of specialty care against which to compare MDC and will uniquely inform the benefit of MDC. Patients in the usual care group will be identified using EMR data accessed through the UPMC Clinical Data Warehouse.

3.2 Inclusion Criteria

3.2.1 Intervention Group

- Patient receiving care at a UPMC Diabetes Outpatient and/or Inpatient settings
- Adult male and female patients 18 to 75 years old
- HbA1c > 7.5%
- Recommended to start self titration of basal insulin
- Access to and able to use an iOs or Android enabled device and have reliable internet access
- Willing and able to use the MDC app
- Able to comprehend basic diabetes survival skills, signs and symptoms of hypoglycemia and treatment of BG

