2.2 Detailed Description of Study Design

2.2.1 Setting

UPMC, headquartered in Pittsburgh, Pennsylvania, is one of the largest integrated health systems in the US, with more than 30 academic, community and specialty hospitals and 600 outpatient sites serving diverse populations throughout the region and beyond. UPMC is closely affiliated with the University of Pittsburgh and together support training for medical residents, clinical trials and other academic research. UPMC's reach and impact are extended through its Health Plan Insurer Services Division, which partners with UPMC and additional community network providers. UPMC is also a recognized innovator in health technology, including developing and applying data-driven approaches to provide patient-centered care. Central to these efforts is UPMC's Clinical Data Warehouse that contains all data points documented within the EMR system for every patient entering a UPMC facility, including but not limited to office visits, hospitalizations, medications, labs, and geographical information. The Department of Clinical Analytics aims to empower UPMC's health care professionals by providing access to interpretable visualizations of their own patient data. Such applications have facilitated both operational- and research-based endeavors, that ultimately improve patient care. For these reasons and more, UPMC provides an ideal "community laboratory" to examine methods that promote access and best practice to the patients it serves.

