2.2.4 Usual Care Group

A retrospective comparative group will be selected from eligible patients who previously were treated at the UPMC Diabetes Outpatient Clinics. This group was chosen for two reasons. First, patients seen at the UPMC Diabetes Specialty Outpatient Clinics have the most robust data available regarding insulin titration, including HbA1c and FBG and, for many patients, BG meter readings. Secondly, this particular group establishes a standard of specialty care against which to compare MDC and will uniquely inform the benefit of this digital tool. We postulate that if MDC produces outcomes, at the very least, equal to those of specialty practice, the likelihood of benefit to PC care is high. Patients in the usual care group will be identified using EMR data accessed through the UPMC Clinical Data Warehouse. As detailed in the Statistical Analysis Plan, propensity score matching will be used to pair intervention and usual care participants.

Study phase			Phase 2 (Maintenance)	
Visits	1	2	3	
Time point	Baseline	3 Months	6 Months	
Visit window		±2 weeks	±4 weeks	
Study Specific Procedures				
Informed Consent	Х			
Eligibility	Х			
MDC Installation and Education	Х	X ¹		
Patient Surveys ³	Х	Х	Х	
Health Care Provider Surveys ⁴	Х	Х	Х	
Reports of Technical Issues		Х	Х	

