3.2.2 Usual Care Group

- Adult male and female patients 18 to 75 years old
- HbA1c > 7.5%
- Started on basal insulin in a UPMC Diabetes Outpatient facility within the past three years of study start

• Has blood glucose data available in EMR (At least two HbA1c measurements corresponding to baseline and a subsequent time point after insulin titration) FBG readings)

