5 RECRUITMENT AND INFORMED CONSENT PROCEDURES

5.1 Recruitment Methods

5.1.1 Intervention Group

Intervention participants will be identified at participating UPMC community-based PC practices, outpatient clinics and inpatient units. A diabetes healthcare provider or staff member (e.g., endocrinologist, PCP, DCES) will identify patients who meet the following inclusion criteria – age, elevated HbA1c, and recommended to start basal insulin – and briefly introduce the patient to the study. The patient may be identified first from a clinic schedule or during the course of their visit. If the patient is interested in learning more about the study, a study investigator (who may also be a diabetes healthcare provider) will provide a more thorough description and a copy of the informed consent for review.

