5.2 Participant Informed Consent Procedures

There are 3 options for obtaining consent:

- 1) Consent process may take place within the diabetes outpatient or primary care setting (Diabetes endocrine satellite clinics or participating primary care sites) or during an inpatient stay.
- 2) Consent process may take place by videoconferencing.
- 3) Consent process may take place by telephone.

Consent will be obtained prior to performing any of the research interventions/interactions.

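### Controls come only from diabetes outpatient clinics, intervention patients also from inpatient units and (on contradictory text) primary care, and the primary comparison never handles setting

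*Combined protocol and SAP*

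**What the plan says.** **Who may enter the intervention group.** The first inclusion criterion in 3.2.1 reads "Patient receiving care at a UPMC Diabetes Outpatient and/or Inpatient settings". Primary care is not named. Three other sections do name it:

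- 3.1: "Intervention participants will be identified in a consecutive manner at participating UPMC community-based PC practices, outpatient clinics and inpatient units".
- 5.1.1 repeats the same three sources and has staff pre-screen on age, raised HbA1c and a recommendation to start basal insulin. Setting is not one of the items checked.
- 5.2: "Consent process may take place within the diabetes outpatient or primary care setting", or during an inpatient stay.

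**Where controls come from.** Section 3.2.2 requires "Started on basal insulin in a UPMC Diabetes Outpatient facility within the past three years of study start". Sections 2.2.4 and 3.1 agree that the comparator is drawn from the diabetes outpatient clinics.

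**Why that comparator.** Section 2.2.4 gives two reasons. Those clinics have the fullest titration data, and they set a specialty-care standard, on the argument that an app which at least matches specialty results would probably help in primary care too.

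**What is balanced or adjusted.** Section 2.6.2 commits the propensity score to age, gender, baseline BMI and baseline HbA1c, with race and comorbidity count as options. The outcome model adds baseline fasting glucose as a fixed effect and matched pair as a random effect. Care setting is in neither.

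**The concern.** There are two linked problems.

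The first is textual. A patient found and consented in a primary care practice follows 3.1, 5.1.1 and 5.2, yet may not meet the setting criterion in 3.2.1. Site staff and the analyst need one answer, because it decides who is enrolled and who is in the primary analysis.

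The second concerns the comparison. Some intervention patients can come from settings that supply no controls. If patients who start insulin in hospital or in primary care would have a different 3-month HbA1c change from specialty-clinic starters even without the app, the between-group difference contains that setting effect as well as any app effect. The primary objective in 1.1.1 attributes the difference to training on and use of the app, so what is at stake is how the primary result may be interpreted.

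**Working it through.** **Step 1. Compare the settings.**

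| Setting | Allowed by 3.2.1 | Recruited under 3.1 and 5.1.1 | Controls available (3.2.2) |
|---|---|---|---|
| Diabetes outpatient | Yes | Yes, if the outpatient clinics meant are the diabetes clinics | Yes |
| Inpatient | Yes | Yes | No |
| Primary care | Not named | Yes | No |

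Only the primary care row is contradictory. The lack of controls affects inpatients whichever text governs, and also primary care patients if 3.1 and 5.1.1 govern.

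**Step 2. Could matching or adjustment deal with it?** All controls have the same setting. For an inpatient or primary care recruit, the probability of being in the intervention group given setting is 1. Putting setting into the propensity model would therefore leave these patients with no comparable control. Overlap can come only from restricting the comparison or widening the control pool.

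**Step 3. Reproduce the planned precision.** Inputs from 2.6.1 and 2.6.2: SD of the 3-month change 1.5, 109 per arm, 95% confidence interval.

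- Standard error = 1.5 × √(2/109) = 0.203.
- Half-width = 1.96 × 0.203 = 0.398, or 0.400 with the t distribution on 216 df.

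This agrees with the stated ±0.40. The formula treats the arms as independent and covers sampling error only.

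**Step 4. Illustrate the bias.** The documents give neither the setting mix nor any setting effect, so both inputs are assumptions. Let *s* be the share of intervention patients from settings without controls (20–50%). Let *d* be the amount by which their 3-month change would differ, without the app, from that of their matched controls (0 to 0.5 points). Then bias = *s* × *d*.

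- *d* = 0: bias 0 at any *s*.
- *s* = 20%, *d* = 0.5: 0.2 × 0.5 = 0.10 points; 0.10/0.40 = 25% of the half-width.
- *s* = 50%, *d* = 0.5: 0.5 × 0.5 = 0.25 points; 0.25/0.40 = 62.5%, about 63%.

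At the upper end, with no app effect, the bias is 0.25/0.203 = 1.23 standard errors, and the 95% interval would exclude zero in about 23% of trials instead of 5%. At zero setting difference the rate stays at 5%.

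**Step 5. Cost of a restricted analysis.** Keep only pairs whose intervention patient was recruited in a diabetes outpatient clinic, with 109 pairs in total.

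- *s* = 20%: 109 × 0.8 = 87 pairs; 1.96 × 1.5 × √(2/87) = 0.45.
- *s* = 50%: 109 × 0.5 = 54 pairs; 1.96 × 1.5 × √(2/54) = 0.57.

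**The case against.** The case for the plan is substantial.

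- **The comparator is a considered choice.** Section 2.2.4 sets specialty care as the benchmark and argues from it to primary care. Anyone who took the clinic-only controls for an oversight would be wrong, and replacing them would change the question being asked. This stands, and it is why the benchmark should be kept. The rationale is about extrapolation, however. It does not say how an app effect would be told apart from a setting effect, and it does not mention inpatients.
- **The contradiction is narrow.** A reader might infer that recruiting outside the clinics breaches 3.2.1 in general, or that the eligible population is undefined. The text supports neither. Inpatients are expressly admitted, and age, HbA1c, insulin recommendation and device access are all specified. Also, 3.1 and 5.1.1 say where patients are identified, whereas 3.2.1 says where they receive care, so a patient identified in primary care who also attends a diabetes clinic would qualify. That resolves some cases. It does not settle those cared for only in primary care, and the protocol does not say that this is the intended reading.
- **The propensity model is described more openly than its list.** Section 2.6.2 says that variables influencing treatment assignment will be included. Setting could be read into that, but Step 2 shows that including it would not help.
- **Care during the study may be similar across sites.** Section 2.2.3 gives intervention patients education from a diabetes educator, and makes educator and endocrinology support available throughout. This may reduce differences in follow-up. It does not address differences between the patients at the start.
- **Same-setting controls may not be usable.** Section 2.2.1 says the warehouse "contains all data points documented within the EMR system for every patient entering a UPMC facility", but 3.2.2 also requires HbA1c at baseline and after titration, and 2.2.4 says the specialty clinics have the most robust data. Feasibility is not shown, so this analysis can only be conditional.

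**Conclusion.** The point holds in two parts. First, 3.2.1 conflicts with 3.1, 5.1.1 and 5.2 on primary care recruits, and on those alone. Second, under either reading some intervention patients may have no control from their own setting, and the analysis plan neither handles this nor checks its effect on the primary HbA1c comparison. Confounding is partial, because patients recruited in diabetes outpatient clinics do have same-setting controls.

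A reader might go further and conclude that the primary estimate is known to be biased, or biased in the app's favour. The documents do not support that: they contain no setting mix and no setting effect, and the direction cannot be determined. The range of 0 to 0.25 HbA1c points (up to about 63% of ±0.40) follows entirely from the assumed 20–50% share and 0 to 0.5 point difference, and it includes zero. What can be said firmly is that the planned interval does not allow for any such effect and that, as written, the plan has no means of detecting one.

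**What to change.** 1. Reconcile 3.2.1 with 3.1, 5.1.1 and 5.2, stating whether patients cared for only in primary care are eligible, and add setting to the pre-screen in 5.1.1.
2. Record the recruiting setting for every intervention patient and report enrolment by setting. The demographic items in 2.2.5 include a location but do not say that it is the recruiting setting.
3. Keep the specialty-clinic comparison as the stated benchmark, and say in 2.6.2 that it is one.
4. Pre-specify a sensitivity analysis of the 3-month HbA1c difference limited to matched pairs whose intervention patient was recruited in a diabetes outpatient clinic.
5. Where the Clinical Data Warehouse holds the required HbA1c pairs for inpatient or primary care starters, pre-specify a supplementary analysis with controls matched on setting.
6. State in advance that, if these analyses disagree with the primary one, the primary difference cannot be attributed to the app alone.

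The cost is an eligibility edit, one recorded variable, a modest amount of extra analysis and, for item 5, a wider record query. The restricted analysis will be less precise: about 54 pairs and ±0.57 if half the intervention patients come from other settings. That makes it a check on the primary result; it would not replace it.

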2 RESEARCH DESIGN AND METHODS

2.1 Classification and Methodological Designs

This study is a 6-month open label non-randomized trial with a prospective intervention group and a retrospective usual care group that includes two phases: Phase 1 (titration) will be used to determine effectiveness of MDC-T during insulin titration after 3 months. This is followed by Phase 2 (maintenance), a 3-month observational period for patients from the intervention group who reach titration targets, to determine effectiveness of their use of the MDC-M in helping patients maintain their glycemic targets. An overview of the study design in shown in the following figure.

Figure 2.1. Study Design

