2.2.5 Study Calendar

Clinical Care/EMR Data Abstraction			
Demographics ⁵	Х		
Patient History ⁶	Х		
Vital signs ⁷	Х	Х	Х
Lab work ⁸	Х	Х	Х
Self-monitoring blood glucose (SMBG)		Х	Х
Provider visits (and Endocrinology escalation visits)		х	Х
Hypoglycemic events	Х	Х	Х
Hospital stays	Х	X	Х
Adverse events	Х	X	Х

1. Education on MDC-M app only for those participants who were able to reach target FBG/A1c transition to maintenance.

2. Diabetes Medication System Rating Questionnaire-Short Form (DMSRQ-SF), Diabetes Distress Scale (DDS17) at all time points; Usability and Satisfaction surveys as 3 and 6 months.

3. Health care provider perspectives and experiences on insulin dosing survey at baseline and usability and satisfaction survey at 3 months and completion of the study.

4. Participant name, age, gender, race, ethnicity, contact information, location, marital status, employment status, education level, health insurance information

5. Diabetes duration, diabetes-related medication, diabetes-related hospitalizations, hypoglycemic events within the past year, co-morbidities

6. Blood pressure, weight, BMI

7. Fasting blood glucose, HbA1c, cholesterol, lipids (if available in clinical records); baseline values may have been collected and recorded up to nine months prior to study start (e.g., lipid panels are usually conducted once a year).

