2.5 Study Endpoints

2.5.1 Primary Endpoint

Change in HbA1c at 3 months as compared to patients using standard of care.

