2.6 Statistical Analysis

2.6.1 Power and Sample Size Justification

The primary objective of this study is to estimate the difference in HbA1c between the study treatment groups at 3 months. The sample size justification is based on precision estimate (i.e., confidence interval for the HbA1c difference between groups). The expected standard deviation for the 3-months change from baseline in HbA1c is 1.5. With 109 patients in the interventional arm and 109 patients in the retrospective control arm, the treatment effect, expressed as the LS means difference between arms, would be estimated with an expected precision of \pm 0.40. Additionally, this sample size allows for a sufficient number of patients after drop-out, loss to follow-up and/or missing data to enter the maintenance phase (Phase 2) of the study. Based on previous research and experiences with insulin titration, an anticipated 70% of patients (n=76) will enter Phase 2 of the study.

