2.6.2 Data Analysis

Patients will be matched 1:1 on a propensity score based on baseline demographics and clinical characteristics to improve the comparability of the interventional and retrospective groups. A logistic regression model will be used to estimate the propensity score and those baseline variables that influence treatment assignment will be included in the model. In this analysis, the following variables will be used to calculate the propensity score: age, gender, baseline BMI and baseline HbA1c. Other factors that may be included are race and number of comorbid conditions. Once the propensity score is calculated, a greedy nearest neighbor algorithm will be used for matching to form pairs of subjects from intervention and control groups with similar propensity scores. This means that for a given treated subject, the closest untreated subject within the specified caliper distance is selected for matching to the treated subject.

Descriptive statistics (e.g., demographics, duration of diabetes, etc.) will be used to describe the study groups. Baseline comparisons will be examined using standardized mean differences. A linear mixed model will be used to adjust the fixed effect of baseline FBG and the random effect of matched pairs, allowing to estimate the treatment effect with 95% CI. . Generalized estimating equations (GEE) for binary outcomes will be for binary outcomes to compare the change in slopes of outcomes of interest between the two groups and account for matched pairs . In addition, for the intervention group only, descriptive statistics will be used to summarize other data (e.g., patient and provider surveys, MDC metrics, etc.), and thematic analysis of any qualitative findings will be made.

Phase 1 (Titration): For the intervention group only, using a descriptive statistical approach, a primary assessment of titration outcomes will be built into the study at 3 months to evaluate the MDC-T app using a combination of clinical data, provider and patient feedback and process data (including patient/provider study-specific efficiency and satisfaction surveys, DE logs, validated DMSRQ-SF and MDC analytics).

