5.2.2 Process for Videoconferencing Consenting

- Study staff sends two copies (one to send back and one to keep) of the consent (via email or USPS) to the potential participant and schedules a video diabetes education visit to occur about a week later. In addition to the consent forms, they will also be provided a self-addressed, stamped envelope.
- During the video visit, the participant must have a hard copy in front of them as the study staff reads it, and if they agree, will sign in front of the study staff by video.
- The participant will hold up their signed signature page and study staff will take a "screen shot" print it out to be attached to the study staff signed consent form. Another option is for the patient to take a picture of their signed signature page and upload into their MyUPMC account for the study staff to access.
- The participant will be instructed to mail their original signed copy of the consent form to study staff using the self-addressed, stamped envelope.

 Research procedures can start via video visit after the study staff gets the screen shot of the participants signature page.

Potential participants are ensured their decision to participate is totally voluntary and in no way will jeopardize their diabetes care or education services. Patients will be given sufficient time to come back to the study team regarding any questions that they may have and their decision. After reading/explaining the consent and study procedures, the study team member will ask the participant if they have any questions (general) and then re-review the study procedures one more time to ensure that they are fully understood.

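### Digital access, willingness, comprehension and consent select the intervention arm only, and no named matching or model variable captures them, so the 3-month HbA1c difference mixes app effect with residual selection

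*Combined protocol and SAP*

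**What the plan says.** Section 2.1 describes an "open label non-randomized trial with a prospective intervention group and a retrospective usual care group". The primary endpoint in section 2.5.1 is "Change in HbA1c at 3 months as compared to patients using standard of care".

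- **Intervention entry (3.2.1, 5.2).** Patients need "Access to and able to use an iOs or Android enabled device and have reliable internet access". They must be willing and able to use the app and "Able to comprehend basic diabetes survival skills, signs and symptoms of hypoglycemia and treatment of BG". Section 5.2 requires consent before any research activity.
- **Control entry (3.2.2, 2.4.1).** Controls are 18 to 75, have HbA1c above 7.5%, began basal insulin at one of the system's diabetes outpatient facilities in the three years before study start, and have at least two HbA1c values, at baseline and later. No digital, willingness or comprehension criterion appears.
- **Exclusions (3.3).** Unwillingness to use the app is an exclusion with no arm named. Nothing says how it would be judged for past patients.
- **Adjustment (2.6.2).** The section gives a general rule that baseline characteristics driving treatment assignment go into the score. It then states that "the following variables will be used to calculate the propensity score: age, gender, baseline BMI and baseline HbA1c", with race and comorbidity count as optional additions. The outcome model adds baseline FBG and a random effect for matched pair.
- **Data listed (2.2.5).** The demographics under EMR abstraction include location and "marital status, employment status, education level, health insurance information". None of these is named for the score or the model.

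**The concern.** Without randomization, attributing the HbA1c difference to the app rests on the two groups being comparable. Here the conditions for entering the intervention arm include traits that have little to do with disease state but may bear on how well a person titrates insulin by any method: having a device and reliable internet, understanding instructions, and volunteering.

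The section 2.6.2 rule would call for these traits, or proxies for them, in the score, because they are conditions of assignment. The named list does not contain them. Any effect they have on HbA1c, beyond what age, gender, BMI, baseline HbA1c and FBG capture, goes into the estimated treatment effect. Section 1.1.1 sets out to demonstrate greater improvement with the app, so this affects the main conclusion. A larger sample would narrow the interval without removing the bias, and section 2.6.2 describes no sensitivity analysis for unmeasured confounding.

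**Working it through.** **Step 1: the plan's own precision.** From section 2.6.1: "The expected standard deviation for the 3-months change from baseline in HbA1c is 1.5", with 109 patients per arm. Section 2.6.2 specifies a 95% interval.

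- SE = SD × √(2/n) = 1.5 × √(2/109) = 0.203
- Half-width = 1.96 × 0.203 = 0.398; with a t quantile on 216 df, 0.400

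The stated ±0.40 is reproduced, so the sample-size figure is not at fault. It describes random error only.

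**Step 2: which entry conditions have a counterpart.**

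| Trait | Intervention | Controls | In score or model |
|---|---|---|---|
| Device and internet | Required (3.2.1) | Not required | No |
| Willing to use the app | Required (3.2.1) | Exclusion in 3.3 has no arm label and no method for past patients | No |
| Comprehension | Required (3.2.1) | Not required | No |
| Consent | Required (5.2) | No consent step described | No |
| Age, HbA1c | Required | Required | Yes |

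**Step 3: what the gap could be worth.** The documents give neither the share of controls with digital access nor its effect on HbA1c. Both are assumed here.

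- p = share of matched controls with access, 60-90%; the intervention arm is 100% by eligibility
- g = effect of access on 3-month HbA1c change, independent of the matched variables and baseline FBG, 0.3-0.5 points
- Bias b = (1 − p) × g
- Coverage of the 95% interval = Φ(1.96 − b/SE) − Φ(−1.96 − b/SE)
- Chance, with no true app effect, that the interval wrongly favours the app = 1 − Φ(1.96 − b/SE); this is 2.5% when b = 0

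| p | g | b | b / half-width | Coverage | Wrongly favours app |
|---|---|---|---|---|---|
| 90% | 0.3 | 0.03 | 8% | 94.7% | 3.5% |
| 80% | 0.3 | 0.06 | 15% | 94.0% | 4.8% |
| 80% | 0.5 | 0.10 | 25% | 92.2% | 7.1% |
| 70% | 0.5 | 0.15 | 38% | 88.6% | 11.1% |
| 60% | 0.5 | 0.20 | 50% | 83.4% | 16.5% |

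The table covers digital access alone. It puts no figure on volunteering or comprehension, and it ignores selection acting the other way.

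**Step 4: whether proxies are within reach.** Section 2.2.1 says the data warehouse holds everything documented in the EMR, geographical information included. Section 2.4.1 expects most data to be available for controls, although the fields it names for them are clinical: HbA1c, FBG, blood pressure, cholesterol and BMI. Location and insurance are therefore reasonable candidates. Completeness of education and employment for controls is unknown.

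**The case against.** An app study has to enrol people who can use the app, and section 3.1 says so openly. The score is also less closed than the four named variables suggest: the general rule in section 2.6.2 leaves room for more, and matching on age and baseline HbA1c removes whatever part of digital ability or self-management is correlated with them. All of this stands. It narrows the problem to a residual, but the plan names nothing aimed at that residual.

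A reader might also infer more than the documents support:

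- **That patients must own a smartphone.** Section 3.2.1 asks for access to a device and the ability to use it.
- **That controls are unfiltered.** Section 3.2.2 filters them in several ways, though not on the traits at issue.
- **That the net bias favours the app.** Requiring a later HbA1c selects controls who came back for care. Section 2.2.4 chooses them as a specialty-care benchmark, while sections 3.1 and 5.1.1 allow intervention patients from primary care and inpatient units. Both features could favour usual care. A possible opposing bias of unknown size does not cancel this one, but the overall sign stays open.
- **That 0.20 is an estimate.** It pairs the two extremes of assumed ranges. A bias as large as the half-width needs 60% access and a full 1.0-point effect, (1 − 0.6) × 1.0 = 0.40, and nothing in the documents supports such an effect.
- **That a portal account is a ready-made matching rule.** Section 5.2.2 mentions it only as a way for a patient to photograph the signed consent page and "upload into their MyUPMC account for the study staff to access". Nothing shows that account status is dated to a control's index date or is a valid marker of digital access. As a primary restriction it could over-select engaged controls.

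**Conclusion.** The concern holds as uncontrolled residual selection. Four entry conditions act on the intervention arm, have no working counterpart among controls, and are not represented by any named variable in the score or outcome model, despite the plan's own rule for choosing score variables. The 3-month difference cannot be read as the app's effect alone.

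The digital and volunteer component plausibly favours the app; the net sign of all selection is undetermined. The range of 0.03-0.20 HbA1c points, 8% to 50% of the stated precision, rests wholly on the assumed prevalence and effect and serves only to show that the issue need not be trivial. Confidence in the structural gap is high; confidence in its size is low. The change should be made because it is cheap, even though it will reduce the selection only in part.

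**What to change.** In section 2.6.2:

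1. Add health insurance type and a residence-based area measure to the propensity score, plus education and employment where the EMR records them for both groups.
2. State how missing values in these fields will be handled.
3. Report standardized mean differences for them after matching.
4. If the warehouse holds a dated marker of digital access, for example an active patient-portal account at the index date, pre-state a sensitivity analysis restricted to controls with that marker. It should not be the primary rule.

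In section 3.3, say which group the unwillingness exclusion covers. In the conclusions, state that the comparison applies to patients with device and internet access.

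The cost is SAP wording and additional fields in the EMR extraction, with no further patient contact. The downside is some missing data and a smaller pool of close matches. Willingness and comprehension will remain unmeasured in controls and should be acknowledged as a limitation.
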